5.6. Patient Reconsent

All patients who are actively participating in the study will be asked to give verbal and written consent again, when the protocol is amended and changes are substantial (e.g., any change that impacts patient safety or the integrity of data). The informed consent will be updated to reflect the protocol changes. Patients who have discontinued will not be required to re-consent but they will be sent a letter from their study site to inform them of protocol or sponsor changes that could be relevant (e.g., a change of study sponsor/MAH or identification of a new, significant drug-related risk).

5.7. Patient Withdrawal

Patients may withdraw consent and discontinue registry participation at any time, without prejudice. Physicians will complete a registry withdrawal case report form (CRF) and all reasonable efforts will be made to establish whether the reason for withdrawal was related to an ADR. Information collected during study participation will be retained for analysis unless the

patient specifically requests otherwise. In the event that a patient discontinues Esbriet treatment prior to registry withdrawal, all SADRs and ADRs of special interest will be collected until 28 days after the last dose of Esbriet or until registry withdrawal, whichever comes first.

6. DATA COLLECTION

Data collection is designed to minimize the burden on the participating physicians, sites, and patients, and to maximize information capture and patient retention. Electronic case report forms (eCRFs) for data entry have been designed to gather specific data consistent with the objectives of the study. If necessary, the physician may also retrieve medical record information from his/her own records and other health care settings. Normally, registry visits will be aligned with routine clinical visits.

6.1. Enrolment/Baseline

Data elements collected at baseline include:

1. Date of informed consent(s)/assent
2. Patient contact information, including secondary contacts and primary health care provider details, if other than enrolling physician
3. Demography [age, gender, race/ethnicity (where allowed by local regulation), smoking history, alcohol use]
4. Medical history and concurrent diseases [including but not limited to hepatic disease, diabetes mellitus, cardiovascular disease (including QT prolongation), kidney disease, other pulmonary diseases (secondary causes of pulmonary fibrosis)]
5. IPF history [date of diagnosis/duration of disease, method of diagnosis (surgical lung biopsy and clinical features, transbronchial biopsy and clinical features, clinical criteria including high resolution computed tomography features), pulmonary function at initiation of Esbriet, prior treatments, oxygen supplementation]
6. Medications used to treat IPF (including but not limited to steroids, immunosuppressive or cytotoxic agents such as cyclophosphamide, azathioprine, alternative therapies such as cyclosporin A, methotrexate, N-acetyl cysteine, sildenafil citrate, bosentan, and interferons)
7. Reason for Esbriet therapy (other than IPF)
8. Initial prescribed dose of Esbriet
9. Concomitant medications
10. Concomitant treatment with warfarin
11. Height and weight
12. Liver function tests

6.2. Follow-up: Years 1 and 2

Data are collected every 3 months (± 4 weeks) during follow-up. The physician or other trained site staff will collect data from the patient during routine clinical visits. The physician will also enter data as necessary from the patient's medical record. In the event that the registry visit does not coincide with a routine clinical visit, the physician, trained site staff, MAH or designated clinical research organization (CRO) registry staff may administer follow-up questionnaires via phone interviews.

The data elements to be collected at follow-up are:

1. Updated contact information
2. Status of prescribed Esbriet treatment (ongoing/dose change/discontinued/reason for change or discontinuation)
3. Changes/additions to other medications used to treat IPF
4. Changes to or addition of warfarin
5. All SADRs and ADRs of special interest (that are considered at least possibly related to Esbriet) and associated information including but not limited to Esbriet dose, concomitant medications, relevant laboratory, clinical, and other test results (See [Section 7.2](#))

6.3. Registry Discontinuation

In discussion and agreement with the EMA and CHMP, the MAH may suspend or terminate the registry or part of the registry at any time for any reason.

6.4. Patients Lost to Follow-up

For patients who discontinue registry participation without notification, before considering a patient lost to follow-up, the physician/site staff will make all reasonable attempts to contact the patient to ensure that the inability to contact the patient is not related to an ADR. If there is no response within a month of the scheduled follow-up visit, site staff, MAH or designated CRO registry staff will contact any other known health care providers to determine if the lack of response is health related and to determine the health status of the patients. If unable to obtain any follow-up data from the other provider(s), site staff, MAH or designated CRO registry staff will contact the secondary patient contact to obtain vital status. The informed consent process and forms outline these procedures, including the possibility of contacting other health care providers. Any data collected prior to loss to follow-up will be included in all analyses.

7. SAFETY EVALUATION AND REPORTING

Any patient who receives at least one dose of Esbriet as part of the registry will be included in the evaluation of safety. When a serious adverse reaction or adverse reaction of special interest is reported, appropriate follow-up measures will be conducted to obtain further information.

7.1. Definition of Adverse Drug Reactions and Serious Adverse Drug Reactions

An ADR is a noxious and unintended response to a medicinal product related to any dose in which a causal relationship between the medicinal product and the adverse event is at least a reasonable possibility. Therefore all SADR and events of interest that are considered at least possibly related to Esbriet will be defined and collected as ADRs.

An SADR is defined as any ADR meeting the following criteria at any dose:

- Results in death;
- Is life threatening (i.e., the patient was, in the opinion of the physician, at immediate risk of death from the event as it occurred); it does not refer to an event which hypothetically might have caused death if it were more severe;
- Requires or prolongs patient's hospitalization;
- Results in persistent or significant disability/incapacity (i.e., the event causes a substantial disruption of a person's ability to conduct normal life functions);
- Results in a congenital anomaly/birth defect;
- Is an important and significant medical event that may not be immediately life threatening or resulting in death or hospitalization but, based upon appropriate medical judgment, may jeopardize the patient or may require intervention to prevent one of the outcomes listed above.

If there is doubt as to whether the event under consideration is a SADR, the event should be treated as a SADR. If the onset of an event occurred before the patient entered the registry in the context of any pre-planned hospitalization (e.g., for cosmetic treatments or for a pre-existing condition) the event should be classified as serious only if in the view of the physician the hospitalization was prolonged or the pre-existing condition worsened as a result of Esbriet treatment.

7.2. Safety Data Collection

The following will be collected from the point of the first dose with Esbriet and will continue through the end of the follow-up period (2 years):

1. SADR
2. Clinically significant ADRs of special interest: These ADRs of special interest encompass all "important identified risks" and "important potential risks" as defined in the Esbriet Risk Management Plan and include:
 - Photosensitivity reactions and skin rashes
 - Abnormal liver function tests
 - Dizziness
 - Weight loss

- Gastrointestinal symptoms
 - Fatigue
 - Falls
 - Drug interactions (including smoking)
 - Increased platelet counts
 - Specific cardiac events: supraventricular tachyarrhythmia, atrioventricular block/sick sinus syndrome, ventricular arrhythmia, bundle branch block, aortic or pulmonic valvular incompetence
 - Blood dyscrasias: agranulocytosis, leukopenia, neutropenia
 - Angioedema
 - Any other clinically significant ADRs based on the judgment of the prescriber
3. Information to be collected in association with reported ADRs (including, but not limited to):
- a. Prescribed Esbriet dose changes and reasons for change
 - b. Concomitant medications including treatments for IPF (those stopped or started within 28 days prior to the event). The following minimum data elements will be collected:
 - Medication name
 - Dose and duration of exposure
 - Indication for use
 - c. Relevant laboratory and clinical tests

In the event that a patient discontinues Esbriet treatment, all SADRs, and ADRs of special interest will be collected until 28 days after the last dose of Esbriet. All serious and reportable ADRs will be followed until resolution or until the end of the follow-up period, whichever comes first.

7.2.1. Other Reportable Information

Pregnancy and/or lactation exposure to Esbriet will be recorded, reported, and followed up. Reportable information includes entire course of pregnancy, delivery, and perinatal and neonatal outcomes, even if there are no abnormal findings. Both maternal and paternal exposures are considered reportable information. For exposure involving the female partner of a male patient, the previously listed information must be collected from the patient with consideration for the partner's right to confidentiality.

7.3. Adverse Drug Reaction Recording and Reporting

Each participating site will be trained on the recording and reporting of SADRs, and ADRs of special interest to the MAH, or designee. Prescribers should follow the local regulations of

reporting ADRs and SADR to local and national authorities. Reportable ADRs include those that are observed by or reported to site personnel by the patient from the time of enrolment through patient discontinuation from the registry (or 28 days after the last dose of Esbriet, whichever is later). The physician or site staff should instruct patients to report ADRs during this time period.

Each patient interview will begin with simple open-ended questions designed to collect information regarding specific reactions of interest. Directly observed ADRs or those reported by patient to the physician or site staff, from time of enrolment (i.e., informed consent has been obtained and patient has received one dose of Esbriet), will be assessed and recorded as appropriate within the CRFs. If a patient is seen by a non-study physician, the study physician and/or trained site staff should make every effort to follow-up with the relevant concerned health care provider to obtain all information necessary for the accurate reporting of the ADR in a timely manner.

Reportable ADRs identified by the physician and/or site staff will be recorded in the ADR eCRF. All SADR should be promptly reported to the MAH within 24 hours of the learning of the ADR. Upon receipt of a SADR or an ADR of special interest, a designated MAH, site or CRO registry staff will initiate appropriate follow-up. All ADRs reported on the ADR eCRF by the reporting physician will be assessed through a follow-up algorithm with the reporting and/or treating physician. If death were to be reported as a suspected ADR, cause of death will need to be ascertained as accurately as possible.

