with a diagnosis of IPF have been enrolled. It is estimated that the enrolment will be completed within approximately 24 months. The Marketing Authorisation Holder (MAH) will closely monitor enrolment and will keep the Rapporteur and Co-Rapporteur informed of progress with the registry at regular intervals. If progress is not satisfactory, then the MAH will discuss with the Rapporteur and Co-Rapporteur any contingency that might be considered in order to increase the recruitment level in the context of the overall usage of the product within the EU. These may include, but are not limited to, extending the registry into another Member State, opening up more sites and intensifying the communication plan.

Each patient will be followed for up to 2 years. The MAH will also closely monitor the retention of patients and will undertake all reasonable efforts and methods to minimize loss to follow-up for the entire 2 years of observation.

Treating physicians will collect pre-specified data at baseline and approximately every 3 months thereafter for the duration of the study. In the event that a patient discontinues Esbriet treatment, all serious adverse drug reactions (SADRs), and adverse drug reactions (ADRs) of special interest will be collected until 28 days after the last dose of Esbriet.

Treatment:

The registry is observational; therefore, all treatment decisions are at the discretion of the patient's health care provider and are not mandated by study design or protocol. Cooperation of health care professionals is based on goodwill and no contractual sanctions will be applied by the MAH.

Inclusion Criteria:

- A clinical decision has been made, prior to study enrolment, to prescribe Esbriet
- Patients who are newly prescribed Esbriet therapy
- Initiation of Esbriet therapy is not more than 30 days prior to study enrolment
- Patient or legal representative provides informed consent and/or informed assent according to local regulations

Esbriet is only indicated for the treatment of mild to moderate idiopathic pulmonary fibrosis in adults. The registry protocol does not encourage use of Esbriet for other conditions or in paediatric patients. However, if a physician, in collaboration with the patient and/or legal representative, makes an independent clinical decision to prescribe Esbriet outside the terms of the Summary of Product Characteristics (SPC), those patients may be included in the registry.

Exclusion Criteria:

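### For patients who stop Esbriet but stay in the registry, the protocol gives two different ends to ADR collection, and the time at risk in Section 9.2.3 does not match the shorter one

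*Protocol*

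**What the plan says.** The protocol describes the end of ADR collection in several places.

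- **Synopsis (Registry Settings):** if a patient discontinues Esbriet, SADRs and "adverse drug reactions (ADRs) of special interest will be collected until 28 days after the last dose of Esbriet".
- **Section 5.7**, for a patient who discontinues Esbriet before leaving the registry: collection runs "until 28 days after the last dose of Esbriet or until registry withdrawal, whichever comes first".
- **Section 7.2, opening:** safety data "will be collected from the point of the first dose with Esbriet and will continue through the end of the follow-up period (2 years").
- **Section 7.2, closing paragraph:** if the patient discontinues Esbriet, "all SADRs, and ADRs of special interest will be collected until 28 days after the last dose of Esbriet".
- **Section 7.3:** reportable ADRs are those observed or reported "from the time of enrolment through patient discontinuation from the registry (or 28 days after the last dose of Esbriet, whichever is later"). The same section adds: "Reportable ADRs identified by the physician and/or site staff will be recorded in the ADR eCRF".
- **Table 1 and Section 8.1:** SADRs and ADRs of special interest are assessed throughout the study and reported at any time during follow-up. Neither mentions a 28-day limit.

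Section 9.2.3 sets the analysis. Cumulative incidence counts patients with an event that starts in the study period, over patients enrolled. The rate is events over cumulative time at risk. Time at risk runs from first dose to completion of follow-up or registry withdrawal and is not cut at 28 days after the last dose.

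**The concern.** Section 5.7 takes the earlier of two dates (registry exit, last dose plus 28 days) and Section 7.3 takes the later of the same two dates. For someone who stops Esbriet they agree only if registry exit falls exactly 28 days after the last dose.

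Two consequences follow for the primary analysis. First, if the 28-day rule is followed, the Section 9.2.3 denominator keeps growing after event collection has ended, and the rate is too low. This happens even if every site applies that rule uniformly. Second, if sites follow different sections, reactions that start more than 28 days after the last dose can be recorded at some sites and not at others. Such reactions fall within the stated objective of monitoring unknown or potential risks.

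**Working it through.** **The protocol's own figures.** The protocol gives no number on this point. Its only calculation, Table 2, reproduces in all eight rows (for example 1.96 × √(0.025 × 0.975 / 1000) = 0.97%) and is not in question.

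**Single patient.** Let L be the day of the last dose and E the day of registry exit.

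- Rule A (synopsis, 5.7, end of 7.2): collection ends at min(L + 28, E).
- Rule B (7.3): collection ends at max(L + 28, E).
- Time at risk (9.2.3) ends at E.

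With E = 730 (a full 2 years):

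| Last dose, day | Rule A ends | Rule B ends | Gap, days | Share of time at risk with no collection under A |
|---|---|---|---|---|
| 90 | 118 | 730 | 612 | 612/730 = 84% |
| 180 | 208 | 730 | 522 | 522/730 = 72% |
| 365 | 393 | 730 | 337 | 337/730 = 46% |

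The rules also conflict, on a smaller scale, for a patient who leaves the registry 7 days after the last dose: 7 days of post-dose collection under Section 5.7 and 28 under Section 7.3.

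**Cohort.** The protocol gives no discontinuation rate, so this part rests on assumptions: a fraction f stops Esbriet by 2 years with constant hazard λ = −ln(1 − f)/2 per year, and all 1,000 patients stay in the registry for 2 years. Put d = 28/365 = 0.077 years. Mean collected time per patient under rule A is

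d + [1 − exp(−λ(2 − d))]/λ.

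- f = 30%: λ = 0.178, collected time 1.705 years. Gap 1000 × (2 − 1.705) = 295 person-years; 295/2000 = 15%.
- f = 50%: λ = 0.347, collected time 1.481 years. Gap 1000 × (2 − 1.481) = 519 person-years; 519/2000 = 26%.

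If every site followed rule A, the Section 9.2.3 rate would be 1.705/2 = 0.85 to 1.481/2 = 0.74 of the rate over the person-time in which events were collected. Under rule B no time at risk is left without collection.

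**Allowing for registry exit.** Assume in addition exponential exit, independent of stopping drug, with a median of 5 or 2 years. These are the ends of the survival range in Section 2, borrowed as an illustration because that range is counted from diagnosis. Total person-time is then 1000 × (1 − exp(−2μ))/μ with μ = ln 2/median, which gives 1,747 or 1,443 person-years.

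| Stop by 2 years | Gap, median 5 years | Gap, median 2 years |
|---|---|---|
| 30% | 246 (246/1747 = 14%) | 188 (188/1443 = 13%) |
| 50% | 433 (433/1747 = 25%) | 333 (333/1443 = 23%) |

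If half of those who stop also leave the registry at about 28 days after the last dose, these person-year gaps halve again.

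**The case against.** The strongest defence is that the opening of Section 7.2 is a general window and its closing paragraph an exception for patients who stop. The synopsis, Section 5.7 and the end of Section 7.2 then agree, and Section 7.3 is the outlier. That is a fair reading of Section 7.2, but it does not remove the conflict with Section 7.3. Nor can Section 7.3 be set aside as a rule on reporting rather than collection, because it sends the reportable ADRs to the ADR eCRF.

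Several stronger readings are tempting and are not supported:

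- **That sites will differ.** All sites are trained on ADR recording and data go into one EDC system. Training or eCRF instructions, which are not shown, may impose one window. The text supports only that sites can differ.
- **That the two windows cannot be separated afterwards.** Table 1 collects the date of the last dose. For patients who stay in the registry both rules require collection up to 28 days after it, so events in that span remain identifiable from their onset dates. Only later events are captured unevenly, and those never collected stay missing.
- **That the rules also clash for a patient who withdraws while still on drug.** The Section 5.7 sentence covers only patients who stop Esbriet before leaving the registry. Section 7.3 does sit awkwardly with withdrawal of consent, but that is a separate point.
- **That person-years translate into events.** Only reactions considered at least possibly related are collected, and few that start long after the last dose may qualify. No change in event counts can be estimated from the protocol.

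It is also true that no hypothesis is tested. But the registry's purpose is to estimate these incidences and rates, so an unmatched numerator and denominator still matters.

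**Conclusion.** The point holds for patients who stop Esbriet and remain in the registry: the protocol states two incompatible ends of ADR collection, and the time at risk in Section 9.2.3 fits only the longer one. Under the 28-day rule the rate is understated. With mixed practice, capture of events beyond 28 days can be uneven.

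Under the stated assumptions (30% to 50% stopping by 2 years, constant hazard, everyone followed for 2 years) the gap is 295 to 519 of 2,000 person-years, or 15% to 26%. These are upper values for those stopping rates, because deaths and withdrawals reduce them. The discontinuation rate is an assumption and not a protocol figure. This should be fixed. It does not invalidate the registry, because the on-treatment window can be recovered.

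**What to change.** 1. Choose one collection window and word it identically in the synopsis, Table 1 and Sections 5.7, 7.2, 7.3 and 8.1. Which window is the sponsor's decision; it must be consistent with withdrawal of consent.
2. In Section 9.2.3, define the event numerator and the time at risk over that same window. Harmonising the collection wording on the 28-day rule without this step would leave the rate diluted.
3. Derive a flag for onset within or after 28 days of the last dose, so that an on-treatment rate can use events and person-time from first dose to last dose plus 28 days, cut at registry exit if earlier, at every site.

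The cost is amendment wording, a memo to sites and one derived variable. The 3-monthly visits and the date of last dose are already in the schedule.

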^a Patients will be interviewed at the specified time points to determine if any of these events have occurred since the last evaluation. However, the study physicians may report an event between evaluations if they become aware that such an event has occurred.

^b Patients may withdraw from the registry at any time following enrolment.

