5.1. Inclusion Criteria

Patients must meet all of the following criteria to be eligible for registry enrolment:

- A clinical decision has been made, prior to enrolment, to prescribe Esbriet; and
- Patient is newly prescribed Esbriet® therapy; and
- Initiation of Esbriet® therapy is not more than 30 days prior to study enrolment; and
- Patient or legal representative provides informed consent and/or informed assent according to local regulations

Esbriet is only indicated for the treatment of mild to moderate IPF in adults. The registry protocol will not encourage use of Esbriet for other conditions or in paediatric patients. However, if a physician, in collaboration with the patient and/or legal representative, makes an independent clinical decision to prescribe Esbriet outside the terms of the Summary of Product Characteristics (SPC), those patients may be included in the registry.

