9.2.3. Primary Analyses

Cumulative incidence of SADRs, and ADRs of special interest will be calculated as the number of patients who have a specific event starting during the study period, divided by the number of patients enrolled, multiplied by 100.

Risk of SADRs, and ADRs of special interest will be estimated as number of events over cumulative time at risk. Time at risk will be defined as the time between dates of first dose of Esbriet to end of follow-up (completion of follow-up / registry withdrawal). Case narratives will be provided for each SADR.

Tables with counts of SADRs, and ADRs of special interest summarized by MedDRA SOC and PT, and stratified by fatal or non-fatal outcome will be provided. Analysis will be conducted, if possible, for subgroups of patients including: predisposing conditions for liver disease; concomitant immunosuppressive therapy and other therapy for IPF; advanced stages of IPF; secondary cause of pulmonary fibrosis; QT prolongation; underlying cardiac, hepatic and other forms of pulmonary disease; Esbriet use for conditions other than IPF; paediatric patients, and patients who have stable warfarin anticoagulation at the beginning of pirfenidone treatment.

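### For patients already on Esbriet at enrolment, reactions between first dose and enrolment can go unrecorded, although Section 9.2.3 counts that interval as time at risk

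*Protocol*

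**What the plan says.** All references are to the protocol.

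- **Entry.** Section 5.1 requires that initiation of Esbriet "therapy is not more than 30 days prior to study enrolment". Section 5.5 also provides for patients who enrol before they are dosed.
- **Collection window.** Section 7.2 opens: "The following will be collected from the point of the first dose with Esbriet".
- **Recording and reporting window.** The first paragraph of Section 7.3 makes reportable those ADRs "observed by or reported to site personnel by the patient from the time of enrolment through patient discontinuation from the registry". Its second paragraph records them "from time of enrolment (i.e., informed consent has been obtained and patient has received one dose of Esbriet" (closing bracket omitted), so enrolment is the later of consent and first dose.
- **Visit content.** None of the twelve baseline items in Section 6.1 concerns ADRs. The synopsis and Section 6.2 list them under follow-up. Footnote a of Table 1 has patients interviewed "to determine if any of these events have occurred since the last evaluation".
- **Analysis.** Section 9.2.3 says that the risk "will be estimated as number of events over cumulative time at risk", and then: "Time at risk will be defined as the time between dates of first dose of Esbriet to end of follow-up". Cumulative incidence in the same section is the number of patients with an event that starts in the study period, divided by the number enrolled. The start of that period is not defined.

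**The concern.** For a patient who enrols on drug, Sections 7.2 and 7.3 can give start dates up to 30 days apart, and only the 7.2 date matches the denominator. The visit content does not settle the matter. There is no baseline ADR item, and at Visit 2 the question about the time since the last evaluation reaches back only to baseline. A site that reads 7.3 as starting at enrolment would add days to the denominator in which it could record no event. A site that follows 7.2 would not.

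At stake are the two primary safety measures of a registry whose only objective is safety. The interval can contain the whole 14-day dose escalation described in Section 2. An analysis plan can choose another denominator, but it cannot recover events that sites never asked about.

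**Working it through.** **1. Start dates side by side**

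| Patient | 7.2 | 7.3, read as starting at enrolment | 9.2.3 time at risk | Gap |
|---|---|---|---|---|
| Enrolled before first dose | first dose | first dose (both conditions must be met) | first dose | 0 |
| Enrolled g days after first dose, g at most 30 (5.1) | day 0 | day g | day 0 | g days |

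**2. The protocol's own precision figures.** Table 2 gives the half-width 1.96 × √(p(1−p)/1000). At p = 2.5% this is 0.97 percentage points and at 20% it is 2.48. All eight rows reproduce. The table does not depend on the start date and serves below only as a yardstick.

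**3. Rate, constant hazard.** Let T be the days from first dose to end of follow-up (730 for the full two years). If no event is recorded in the first g days but those days stay in the denominator, observed rate / true rate = 1 − g/T. The relative loss is g/T:

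| T (days) | g = 30 | g = 15 |
|---|---|---|
| 730 | 4.1% | 2.1% |
| 365 | 8.2% | 4.1% |
| 180 | 16.7% | 8.3% |
| 90 | 33.3% | 16.7% |

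**4. Cohort.** If all 1,000 patients had g = 30 and T = 730, 1000 × 30/365.25 = 82 of 1000 × 730/365.25 = 1,999 patient-years could carry no events, again 4.1%. If a share f of patients enrols on drug and follow-up is similar in both groups, the cohort loss is f × 4.1%. With f assumed to be 50%, for example, it is about 2.1%. The protocol gives neither f nor the distribution of g.

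**5. Rate, front-loaded hazard (assumption).** If the hazard in days 1 to 30 is k times the later hazard and g = 30, the share of expected events lost is 30k/(30k + T − 30):

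| T (days) | k = 1 | k = 3 | k = 5 |
|---|---|---|---|
| 730 | 4.1% | 11.4% | 17.6% |
| 365 | 8.2% | 21.2% | 30.9% |
| 180 | 16.7% | 37.5% | 50.0% |

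The values of k are illustrative and none comes from the protocol.

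**6. Cumulative incidence.** Its denominator is patients, so time at risk plays no part. A patient is lost only if no later event of the same kind starts. With constant hazard and T = 730, the 4.1% event loss is therefore an upper limit: at most 0.041 × 2.5 = 0.10 percentage points on a 2.5% reaction (Table 2 precision 0.97) and 0.041 × 20 = 0.82 on a 20% reaction (precision 2.48), even if every patient had the full gap.

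**7. Effect of a common start.** With constant hazard λ, and with events and time both starting at enrolment, the rate is λ(T − g)/(T − g) = λ, so the understatement disappears.

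**The case against.** The strongest reply is that 7.3 dates the report and not the onset. It speaks of ADRs observed or reported from enrolment and has staff tell patients to report in that period. A rash that began on day 5 and was mentioned at enrolment on day 30 would fall inside it. On that reading 7.2 sets the onset window, 7.3 sets the reporting channel, and nothing need be lost. Other text points the same way. Table 1 has serious ADRs (SADRs) and ADRs of special interest assessed over the whole study. Section 7.3 starts every patient interview with open-ended questions on reactions of interest and does not exempt baseline. Table 1 also ticks dose changes and their reasons at baseline.

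This stands in part, and it makes the loss possible rather than certain. A reader might infer that 7.3 bars all events before enrolment and that both primary measures are therefore biased low. The text does not go that far. It does not exclude that reading either. The open-ended questions are not tied to the interval since first dose, a reason for a dose change is not an ADR record with an onset date, and Section 9.2.3 leaves the start of the study period undefined.

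It is also fair to say that the constant-hazard effect is small against Table 2, that no hypothesis is tested, and that patients enrolled before dosing are unaffected. A reader might take the 30% to 50% losses above as the likely size. They need the maximum gap, assumed front-loading and short follow-up together, and the protocol supports none of these as typical.

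**Conclusion.** The point holds as a gap in the collection rules that can bias results downward. It does not show that bias has occurred. For a patient enrolled on drug, if sites read 7.3 as starting at enrolment, the event rate is understated by up to 4.1% relative (30-day gap, 730 days, constant hazard). The figure is larger only under assumed shorter follow-up or front-loading. Cumulative incidence is understated only through patients whose sole event of a given kind falls in the gap. The effect on the whole registry scales with the share enrolled on drug, which is not given. Table 2 is unaffected.

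A reader might also infer that the primary rate must be recomputed from enrolment. That is needed only if events before enrolment are not collected. Once they are, the first-dose start in Section 9.2.3 is consistent with the numerator.

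**What to change.** 1. **Section 7.3.** Keep the consent condition, and add that once consent is obtained, all SADRs and ADRs of special interest with onset on or after the first dose are recorded, including those before enrolment. Simply replacing enrolment with first dose would drop that condition and conflict with Sections 5 and 10.2, which put consent before any data collection.
2. **Section 6.1 and Table 1.** For patients already on drug, add a baseline question on these reactions from first dose to enrolment, with onset dates.
3. **Section 9.2.3.** Define the study period as starting at first dose.
4. **Sensitivity analysis.** Report the rate with events and time at risk both starting at the later of first dose and enrolment. For patients already enrolled without the baseline question, this is the rate whose numerator and denominator match. It uses the consent date (already in 6.1), the first-dose date (already needed for 9.2.3) and the onset dates of recorded events. It says nothing about the unobserved early days themselves.

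The cost is a few sentences, one extra eCRF item and one extra analysis row. The downside is recall over at most 30 days.
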